4.1. Dose and Treatment Schedule

Subjects will be randomized 2:2:1 to receive one of two doses of EDP-305 or placebo. Every subject will receive a single daily dose of blinded study drug for a total of 12 weeks. An overview of the study design is shown in [Figure 1](#). Study visits and assessments are detailed in the Schedule of Assessments (SoA) ([Table 19](#)).

Figure 1. Study Design

Abbreviations: D=Day; W=Week

4.2. Rationale for Study Design

This proposed study will evaluate EDP-305 in patients with NASH who will be randomized to one of three treatment groups: (1) 1 mg EDP-305, (2) 2.5 mg EDP-305, or (3) placebo in a 2:2:1 ratio.

4.2.1. Justification of Design and Control Group

Currently, there are no approved pharmacologic therapies for this disease. The recommended first-line nonpharmacologic therapy is lifestyle modification through dietary modification and increased physical activity (*Ratziu, 2013*).

Based on nonclinical and *in vitro* data, EDP-305 is an FXR agonist which plays an essential role in the feedback regulation of BA biosynthesis and given the critical role BAs play in liver homeostasis, FXR has become a target for therapeutic intervention in NASH.

[REDACTED]

This Phase 2 study aims to evaluate safety, tolerability, and PK/PD (ie, dose selection) of the investigational novel FXR agonist, EDP-305 in a targeted patient population with presumptive presence of NASH by either a prior liver biopsy or phenotypic characteristics but no liver biopsy at entry. Subjects will have confirmed presence of NASH by histologic evidence on a prior liver biopsy within 24 months and elevated ALT, OR phenotypic diagnosis of NASH based on elevated ALT, BMI (>25 kg/m² or >23 kg/m² for Asian-Americans), and diagnosis of T2DM or pre-diabetes. These subjects at high risk for NASH will be assessed based on evidence of fatty liver, two components of the metabolic syndrome, and evidence of liver fat and stiffness by imaging.

This double-blind phase of this study is being conducted for 12 weeks. Based on the mechanism of EDP-305 and, on observed data in other short-term treatment Phase 2 studies that were published with similar therapies (*Neuschwander-Tetri et al., 2015*), the Sponsor believes that liver enzyme reductions and change in noninvasive biomarkers (imaging and metabolic/mechanistic markers) will be seen after >1 month of therapy.

[REDACTED]

The purpose of the double-blind design is to obtain the most unbiased assessment of clinical safety and efficacy with the doses being studied. To assess changes in liver fat and fibrosis an MRI and MRE will be conducted during the screening period and at the end of treatment. Additionally, markers for liver fibrosis and inflammation, cardiovascular markers, and biomarkers for NASH will be evaluated throughout the study and changes from baseline evaluated.

[REDACTED]

4.2.2. Justification of EDP-305 Dose

This phase 2 study has been designed to assess the efficacy, safety and tolerability of 2 doses (1 mg and 2.5 mg) of EDP-305 in patients with NASH [REDACTED]

[REDACTED]

[REDACTED]

[REDACTED]

[REDACTED]

5. STUDY DRUG AND TREATMENT OF SUBJECTS

5.1. Description of Study Drug

EDP-305 drug product tablets consist of 1 mg and 2.5 mg strengths supplied as [REDACTED]

[REDACTED] Matching placebos for the two strengths will also be supplied [REDACTED]

[REDACTED] Study drug and matching placebo tablets will be supplied by Enanta.

[REDACTED]

[REDACTED]

[REDACTED]

Additional information will be provided in the Pharmacy Manual.

5.2. Packaging and Labeling

EDP-305 tablets and matching placebo will be supplied in high density polyethylene bottles [REDACTED]. All bottles containing clinical trial material will be labeled according to study drug labeling in compliance with applicable local and national regulations for labeling of investigational products.

EDP-305 tablets are packaged in a [REDACTED]

5.3. Storage

5.4. Accountability

[REDACTED]

Study drug may be dispensed only under the supervision of the investigator or authorized designee and only to study subjects. The Pharmacist or designated study staff will maintain adequate records of 1) study drug received, 2) study drug dispensed to the subjects, and 3) drug returned by the subjects. Subjects will be instructed to return all used and unused study drug to the site. All used and unused study drug will be retained at the site according to instructions provided by Enanta or designee until monitored by the study monitor. The study monitor will review study drug records and inventory throughout the study.

5.5. Handling and Disposal

Study drug must not be used for any purpose other than for administration to subjects enrolled into this clinical study. All study drug bottles that are opened and returned by subjects as well as those that are not opened or assigned to subjects will be retained at the site according to instructions provided by Enanta or designee until monitored by the study monitor. Full accountability of all study drug distributed to patients will be documented per Section 5.4.

At the end of the study, Enanta will provide instructions for the destruction of any unused study drug. If Enanta authorizes destruction at the study site, the Investigator must ensure that the materials are destroyed in compliance with applicable environmental regulations, institutional policy and any special instructions provided by Enanta, and, that the destruction was adequately documented.

5.6. Treatment Assignment/ Randomization

Subjects will be randomized to study treatment using an Interactive Web Response System (IWRS). [REDACTED]

[REDACTED] Subjects will be randomized to the treatment groups shown below:

- Treatment Group 1 (N=50); EDP-305 1 mg orally for 12 weeks
- Treatment Group 2 (N=50); EDP-305 2.5 mg orally for 12 weeks
- Treatment Group 3 (N=25); Placebo (PBO) orally for 12 weeks

[REDACTED] The randomization code will be produced by Enanta (or designee). The Enanta unblinded biostatistician or designee will review and approve the final randomization list.

During the Screening period, subjects will be identified by a unique screening number assigned by the clinical site. Subjects who have completed screening assessments and are eligible for participation in the study will be randomized before the first dose of study drug (Day -1 or Day 1) and assigned a unique subject number which will be used to identify the subject throughout the study.

5.7. Study Drug Dose and Administration

Complete instructions for dispensing and administering study drug are presented in the study specific Pharmacy Manual.

The subject will be instructed to take all study drug doses at home except when study drug will be administered in the clinic (ie, at the Days 1 and 3, and Weeks 2, 4, 8 and 12 visits). The subject will be instructed to take the study drug approximately at the same time every day (ie, orally in the morning after fasting overnight for a minimum of 8 hours). If a subject forgets to take their study drug at their scheduled time, the dose may be taken later that day following a minimum of 4 hours fast; however, no more than 1 dose should be taken on any calendar day and a minimum of 16 hours between doses should be maintained.

[REDACTED]

5.7.1. Dispensing of Study Drug

When drug is dispensed at the clinic, study drug may be dispensed only under the supervision of a qualified pharmacist or an authorized designee and only for administration to the study subjects.

[REDACTED] The bottle number dispensed to the subject and the number of tablets dispensed will be recorded in the site source documents. [REDACTED]

5.7.2. Treatment Compliance

The subject will be instructed to bring all study drug (including empty bottles) to the clinic at each study visit. Both accountability and study drug compliance will be reviewed at each visit as indicated in the SoA (Table 19). The number of tablets will be counted and the study personnel will ask the subjects why any doses were missed, if applicable. Any potential reasons for lack of compliance with dosing will be monitored and followed up by the study personnel.

For any subject demonstrating continued noncompliance of study drug dosing despite continued educational efforts, the investigator should contact the study medical monitor to discuss possible discontinuation of the subject from the study.

5.8. Concomitant Medications

All subjects enrolled in the study must abstain from taking any prohibited concomitant medication through the end of study.

Subjects taking Vitamin E and antidiabetic medications should be on a stable dose for at least 3 months prior to screening.

Details of prior and concomitant medication use will be recorded in the source documentation and the electronic case report form (eCRF) as indicated in the SoA (Table 19).

5.8.1 [REDACTED]

5.9. Prohibited Medications

Inhibitors and inducers of CYP3A4 and P-gp are prohibited within 14 days prior to the first dose of study medication and throughout study duration.

A comprehensive list of CYP3A4 inducers and inhibitors can be found at:

<http://medicine.iupui.edu/clinpharm/DDIs/ClinicalTable.aspx>

Additionally, medications that inhibit or induce the transporter proteins P-gp are also prohibited during study participation. A list of these medications can be found at

<http://bts.ucsf.edu/fdatransportal/index/>.

Use of a new statin regimen is prohibited from Screening and throughout study duration. Subjects on a stable dose of statins for at least three months prior to Screening are allowed. However, no dose modification during the study will be allowed.

Use of a new antidiabetic regimen from Screening and throughout study duration, including metformin, GLP-1 agonists, sodium-glucose cotransporter-2 (SGLT2) inhibitors, sulfonylureas, or dipeptidyl peptidase-4 (DPP4) inhibitors, insulin or peroxisome proliferator-activated receptor (PPAR) γ agonists (pioglitazone or rosiglitazone). **For pre-existing antidiabetic treatment**, subjects should be on a stable dose of antidiabetic drugs: (1) for at least 2 months (for metformin and/or sulfonylureas), (2) 3 months (for SGLT2 or DPP4 inhibitors), or (3) 6 months (for GLP-1 receptor agonists and thiazolidinediones) prior to Screening. NOTE: Sulfonylureas and insulin are only permitted if glycemia is self-monitored by the subject; subjects treated with insulin are eligible if clinically stable on insulin treatment (ie, no recurrent acute hypo- or hyperglycemic episodes diagnosed clinically with serum glucose levels of <50 mg/dL or >200 mg/dL) for at least two months prior to Screening.

5.10. Other Restrictions

Table 14 outlines protocol restrictions other than prohibited medications outlined above and the timing of those restrictions.

Table 14: Protocol Restrictions

Restricted Medication/Food/Activity	Timing of Restriction	
	From (minimum)	To
Experimental treatment for NASH	6 months prior to Screening	End of Study Visit
OCA	Any prior or concurrent use	End of Study Visit
Immunosuppressants (eg, corticosteroids) for more than 2 weeks	1 year prior to Screening	End of Study Visit
New statin regimen	3 months prior to Screening	End of Study Visit
Experimental or unapproved drugs	Within 1 year of Screening	End of Study Visit
Investigational agent or vaccine*	30 days prior to first dose of study drug	End of Study Visit
Biologic Product	3 months (or 5 elimination half-lives) prior to first dose of study drug	End of Study Visit
New antidiabetic regimen of metformin and/or sulfonylureas	2 months prior to Screening	End of Study Visit
New antidiabetic regimen of insulin	2 months prior to Screening	End of Study Visit

Restricted Medication/Food/Activity	Timing of Restriction	
	From (minimum)	To
New antidiabetic regimen of SGLT2 inhibitors	3 months prior to Screening	End of Study Visit
New antidiabetic regimen of DPP4 inhibitors	3 months prior to Screening	End of Study Visit
New antidiabetic regimen of GLP-1 receptor agonists or thiazolidinediones	6 months prior to Screening	End of Study Visit

*Flu vaccine will be allowed upon Medical Monitor's approval

6. BLINDING

The study will be double-blinded meaning the subjects, Investigators, and site staff will be blinded to treatment assignment until the completion of the study.

All study personnel will be blinded to treatment assignment except for the following individuals:

- Unblinded Enanta/Clinical Research Organization (CRO) statistician for purpose of generating and monitoring the randomization list
- Unblinded Drug Supply Chain personnel for the purpose of monitoring drug supplies
- Enanta/CRO Pharmacovigilance Group and Regulatory Affairs representatives when required to satisfy regulatory reporting requirements
- Bioanalytical Laboratory for the purpose of measuring drug concentrations

6.1. Blinding of Study Samples

6.1.1. Blinding of NASH Biomarkers, Fibrosis and Inflammatory Markers, MRI/MRE, and Laboratory Liver Test Results

Investigators, site personnel, and CRO/Sponsor will be blinded to the following laboratory tests postbaseline:

- Biomarker laboratory data
 - FGF-19, total BAs
 - C4 [7 α -OH-4-cholesten-3-one]
 - CK18
 - GLP-1
- Fibrosis and inflammatory markers
 - ELF Panel (ie, hyaluronic acid [HA], procollagen III amino terminal peptide [PIIINP], and tissue inhibitor of metalloproteinase 1 [TIMP-1])
 - PRO C3
 - Fibrinogen, CRP, alpha2 macroglobulin and Haptoglobin
 - Tumor necrosis factor alpha and beta (TNF- α and β)
 - Interleukin (IL)-6. IL1 β
 - APRI
 - NFS
 - FIB-4
- Liver Tests
 - ALT

- AST
- GGT

However, abnormal liver test results will be flagged if the lab results are $\geq 2 \times$ baseline and these flagged results will be shared with the Investigator and the Medical Monitor (and/or designee) for safety monitoring purposes.

MRI and MRE results postbaseline will be blinded to the Investigators, site personnel, and Sponsor. Additionally, the MRI facility and radiologist will be blinded to the subject's study treatment and the MRI and MRE readings will be read centrally.

6.1.2. Blinding of Pharmacokinetic Samples

All PK sample concentration measurements will be blinded to the Investigators, site staff, and study subjects. The laboratory performing bioanalytical analysis, however, will be provided the randomization scheme.

6.2. Unblinding

At the initiation of the study, the study site will be instructed on the method for breaking the blind. The unblinding method will use the IWRS process.

Unblinding of individual subject treatment by the investigator should be limited to medical emergencies or urgent clinical situations in which knowledge of the subject's study treatment is necessary for clinical management. In such cases, the investigator must first attempt to contact the study medical monitor to discuss and agree to the need for unblinding. In situations in which investigator have attempted and failed to contact the medical monitor, and/or the urgency of the case required immediate action, investigators should use their best judgment, based on the nature and urgency of the clinical situation, and proceed with unblinding.

- For unblinding, in the event the local [REDACTED] medical monitor cannot be reached, sites at all locations should call the following 24/7 global medical coverage hotline: [REDACTED]

Once a subject's treatment assignment has been unblinded for a medical emergency or urgent clinical situation, the medical monitor and study coordinator should be notified within 24 hours of unblinding of the treatment. Information relating to unblinding (eg, the reason, date) should be clearly recorded in the subject's study file. In addition, the Investigator should consider whether the clinical event that prompted unblinding should be considered a serious adverse event (SAE), according to the regulatory definitions or criteria for SAEs, and if so, submit an SAE report as described in [Section 9.2](#).

The Safety and Risk Management group will also unblind any SAE reports in compliance with regulatory reporting requirements. In addition, Enanta may unblind individual subjects at any time for matters relating to safety concerns.

NOTE: Investigative sites will be provided country-specific toll-free telephone numbers.

7. STUDY CONDUCT AND VISIT SCHEDULE

7.1. Study Visits

Details of assessments at each visit are presented in the SoA ([Table 19](#)).

7.1.1. Screening

Screening procedures will occur after the subject signs and dates an Institutional Review Board (IRB) or Ethics Committee (EC) approved informed consent form (ICF) and provides authorization to use protected health information (See [Section 12.1.3](#)). The ICF will be completed prior to conduct of any study-specific procedures.

Screening procedures will be conducted as listed in the SoA ([Table 19](#)). Screening will occur over a period lasting no more than 28 days. For each subject, Screening can occur on one day or over multiple days. All Screening assessments must occur no earlier than 28 days before the first dose of study drug at the Day 1 visit. If any Screening assessment falls outside of that window, the Investigator should consult with the Sponsor's Medical Monitor to determine if the assessment needs to be repeated.

If a subject does not qualify for study entry due to an out-of-range lab value that is not consistent with the subject's medical history or appears spurious, with the approval of the Medical Monitor, the subject may retest that lab parameter once if the Investigator believes that he/she would qualify upon retest.

At the completion of Screening procedures/assessments, subjects who qualify for the study should be given detailed instructions on fasting requirements prior to the first dose and when to return to the clinic for the Day 1 visit.

7.1.2. Rescreening

Subjects who met all eligibility criteria that were current at the time of their Screening Visit may be rescreened under the following circumstances with the approval of the Medical Monitor:

- Subjects within the Screening Period who met all eligibility criteria, but are not able to obtain required documentation within the allotted window for the Screening Period.
- Subjects who are eligible, but transiently (for personal reasons) unable to commit to all study procedures.
- Subjects who have abnormal laboratory results, which may potentially reflect erroneous results, based on Investigator judgement.

7.1.3. Baseline (Day 1)

Subjects who meet all inclusion criteria and none of the exclusion criteria will report to the clinic on the morning of Study Day 1 after fasting overnight for a minimum of 8 hours. After a review of applicable inclusion and exclusion criteria, subjects who continue to satisfy eligibility

requirements will be randomized in a 2:2:1 ratio to their treatment group. Predose assessments and procedures will be conducted as noted in the SoA (Table 19) and considered Baseline values.

After predose study procedures are completed, subjects will receive the first dose of study drug in the clinic on Day 1 followed by PK and biomarker blood draws. [REDACTED]

[REDACTED] K and PD samples will be collected as described in SoA (Table 19).

Before leaving the clinic, subjects will receive study medication and instructions on how to take the medication at home.

7.1.4. Treatment Period Visits (Day 3, Weeks 2, 4, 8, and 12/EOT)

All subjects will be requested to return to the clinic on Days 3, and Weeks 2, 4, and 8 for on-treatment study visits. Subjects will be instructed to fast overnight for a minimum of 8 hours prior to each visit. Except for days when there is a clinic visit, subjects will take their daily dose of study drug at home. Treatment period assessments are listed in Table 19.

At the end of the treatment period, subjects will complete the EOT visit. Subjects who complete 12 weeks of treatment will complete the EOT assessments at the Day 84 (Week 12) visit. Subjects who discontinue treatment early should complete EOT assessments at the time of discontinuation (if in the clinic) or as soon thereafter as possible if the subject discontinues treatment while not in the clinic. Procedures performed are specified in the SoA (Table 19).

Subjects should discontinue drug on Day 84. Subjects, who return for their EOT Visit after Day 84, should stop dosing on Day 84 (Week 12 Visit).

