2.2.2. Secondary Endpoints

The secondary endpoints of the study are as follows:

- Change from Baseline in percentage of fat in the liver as assessed by magnetic resonance imaging-estimated proton density fat fraction (MRI-PDFF) at Week 12
- Change from Baseline in liver stiffness as assessed by magnetic resonance elastography (MRE) at Week 12

- Change from Baseline of noninvasive liver fibrosis markers (Enhanced Liver Fibrosis [ELF] panel) and PRO C3 at Week 12
- Change from Baseline in NAFLD Fibrosis Score (NFS), AST to Platelet Ratio Index (APRI), and fibrosis 4 (FIB-4) at Week 12
- Change from baseline in TG, total cholesterol (TC), high density lipoprotein cholesterol (HDL-C), low density lipoprotein cholesterol (LDL-C), adiponectin and apolipoproteins (Apo)A1, B, C3 at Week 12
- Change from Baseline in fasting glucose and insulin, HOMA index (in nondiabetic subjects) and glycated hemoglobin (HbA1c) in subjects with Type 2 diabetes mellitus (T2DM) at Week 12
- Change from Baseline in fibrinogen, CRP, IL6, IL1 β , TNF- α , TNF- β , alpha2 macroglobulin, and haptoglobin levels at Week 12
- Pharmacokinetic parameters of EDP-305 (and metabolites): C_{max} , t_{max} , and AUC_{last}
- Change from Baseline in body weight at Week 12
- Change in WTH ratio at Week 12
- Pharmacodynamic parameters of EDP-305: FGF19, C4, and bile acid (BA) at Week 12

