7.1.5. Safety Follow-up Period (End of Study Visit)

All subjects, including those who discontinue treatment early, should return to the clinic for the EOS visit 4 weeks after the last dose of study drug for follow-up safety assessments (Table 19). For subjects who complete the study, the EOS visit would be scheduled on Day 112.

Any subject with ongoing AEs/SAEs at the EOS visit should be followed until resolution of their AE/SAE or until the Investigator has determined that the event has stabilized as discussed in Section 9.3.

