8.4.3. Pharmacokinetic Samples

Plasma samples will be collected and processed to define the PK parameters according to the procedures provided and/or approved by Enanta Pharmaceuticals, Inc. Plasma PK samples will be collected as shown in the SoA (Table 19). More detailed information will be given in the Laboratory Manual.

Population PK (for subjects not participating in PK/PD Substudy): On scheduled visits at Day 1, and Weeks 2, 4, 8 and 12, PK samples will be collected at three timepoints: predose and at two timepoints postdose; the first postdose sample collected 1 to 3 hours postdose and the second postdose sample collected at least one hour later. Where possible, the samples at each visit should be obtained at different times postdose relative to each other.

PK Sampling for Subjects with Transaminase or ALP Elevations: Subjects with persistent transaminase or ALP elevations, and have evidence of liver injury, additional PK samples will be collected at each visit where safety labs are obtained (see Section 10.2).

More detailed information will be given in the Study Manual. It is important that the date and time of each of the PK blood samples are accurately recorded in the source document.

Within 8 hours postdose, an acceptable window around each PK draw is ± 10 minutes. Predose PK samples should be drawn within 30 minutes of the next scheduled dosing time. Actual date and time of PK sample collection will be recorded in the eCRF. In addition, the site should record the time of last dose taken at home prior to the visit.

PK samples may be stored and used for future metabolite identification and/or further evaluation of the bioanalytical method. These data will be used for internal exploratory purposes and will not be included in the clinical study report.

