14. APPENDICES

Table 19: Schedule of Assessments

Study Event	Screening ¹	Study Assessments per Planned Study Day						EOS
Visit Day	D-28 to -1	D1 ²	D3	D14±2	D28±2	D56±2	D84±3 ³	D112±2
Treatment Week⁴				W2	W4	W8	W12/EOT ⁵	W16
ICF ⁶ ; Demography ;Medical History	x							
Inclusion/Exclusion	x							
FSH ⁷ ; HIV,HCV, and HBV	x							
Pregnancy Test ⁸	x	x			x	x	x	x
Height, Weight and BMI ⁹	x	x					x	x
Physical Exam ¹⁰	x	x	x	x	x	x	x	x
Vital Signs ¹¹	x	x	x	x	x	x	x	x
Oral Temperature	x	x						x
ECG	x	x	x		x		x	
Waist to Hip Ratio		x					x	
Safety Lab. Tests ¹²	x	x	x	x	x	x	x	x
PT/PTT and INR	x							x
CV Markers ¹³		x		x	x	x	x	x
MRI-PDFF, MRE	x						x	
ELF Panel, PRO C3, Inflammatory Markers ^{14, 15}		x					x	
APRI, FIB-4, and NFS		x					x	
FGF-19, C4, BA, and ALT ¹⁶		x		x	x	x	x	
PK/PD sub study (PK, C4, FGF-19, BA, and ALT) ¹⁷		x		x	x	x	x	
Population PK samples ¹⁸		x		x	x	x	x	
CK-18 and GLP-1 ¹⁵		x		x	x	x	x	
Study Drug Dosing ¹⁹		Daily Dosing						
Drug Accountability			x	x	x	x	x	
AE/SAE & Con Meds	x	x	x	x	x	x	x	x
Exploratory research samples ¹⁵		x			x	x	x	

1. Screening assessments should be conducted within 28 days prior to the first dose of study drug (ie, Study Days -28 to -1)
2. On Day 1, all samples are to be collected predose with the exception of post dose PK and PD samples
3. Subjects should discontinue drug on Day 84. Subjects who return for their EOT Visit after Day 84, should stop dosing on Day 84
4. For the treatment phase, indicates number of completed weeks of treatment
5. For the EOT visit for subjects who discontinue early, all procedures for the Week 12 visit will be conducted; however, an MRI /MRE will not be performed if the subject has discontinued study drug prior to Day 14 and only 1 PK sample will be obtained. Subjects who discontinue the study early should complete the EOT procedures as soon as possible and return 4 weeks later for the EOS visit. For subjects with persistent transaminase elevations and who discontinue study drug with evidence of liver injury, additional PK samples will be collected at each visit where safety labs are obtained
6. Informed consent must be obtained prior to conducting any study-specific procedures or assessments
7. For post-menopausal women only
8. Serum pregnancy test at Screening and Baseline, and urine pregnancy testing at Baseline and all other visits. If the urine pregnancy test is positive, a serum pregnancy test should be obtained as soon as possible to confirm.

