9. Height to be assessed at Screening only
10. Full physical exam (PE) at screening and EOS Visit; subsequent PE should be targeted to review new signs and symptoms
11. Vital Signs include heart rate, respiratory rate, blood pressure, and will be measured once in the morning before the morning dose of study drug
12. Safety laboratory tests include chemistry (including liver function tests), hematology, and urinalysis and should be collected predose at all visits; See [Table 15](#) for details. Creatinine clearance will be calculated based on serum creatinine value performed all visits.. HbA1c will be obtained at Screening, Baseline, and Week 12 only
13. Lipids and CV risk markers to be collected are detailed in [Table 15](#)
14. Markers of inflammation include fibrinogen, CRP, IL6, IL1 β , TNF- α , TNF- β , alpha2 macroglobulin and haptoglobin (See [Table 15](#))
15. Samples will be collected from all subjects predose. Additional samples may be collected to further assess safety events.
16. Samples should be collected after a minimum 8 hr fast and before the subject takes the daily dose of study drug. All samples collected Day 1, Weeks 2, 4, 8 and 12 at predose and two samples postdose; with the first sample collected 1 to 3 hours postdose and the second sample collected at least 1 hour later
17. Collect PK/PD samples after a minimum 8 hr fast and before the daily dose of study drug. PK/PD samples on Days 1 and 84 (Week12) collected predose and 2, 6, and 8 hr postdose; Weeks 2, 4 and 8 at predose and two samples postdose with the first sample collected 1 to 3 hours postdose and the second sample collected at least 1 hr later
18. PK predose samples should be collected after a minimum 8 hour fast before the daily dose of study drug. PK samples collected Day 1, Weeks 2, 4, 8 and 12 at predose and two samples postdose; the first sample collected 1 to 3 hours postdose and the second sample at least 1 hour later. For subjects with persistent transaminase or ALP elevations, and have evidence of liver injury and who remain on study drug, [REDACTED].
19. Study drug given in the clinic on days where subject is seen in the clinic

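### A completer seen for Week 12 on Days 85–87, as the visit window allows, has already stopped dosing under Section 7.1.4, so the specified post-dose PK/PD samples cannot be taken and a Day 86–87 predose sample is not a 24 h trough

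*Protocol*

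**What the plan says.** **Visit window and stop rule.** Protocol Table 19 sets the Week 12/EOT visit at Day 84 ± 3. Section 7.1.4 foresees a visit after Day 84 and says "Subjects, who return for their EOT Visit after Day 84, should stop dosing on Day 84". Footnote 3 repeats this: "Subjects who return for their EOT Visit after Day 84, should stop dosing on Day 84".

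**Clinic dosing.** Section 5.7 says "study drug will be administered in the clinic (ie, at the Days 1 and 3, and Weeks 2, 4, 8 and 12 visits". Footnote 19 likewise has drug given on any day the subject is in clinic. Neither makes an exception for Days 85–87.

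**Sampling at Week 12.** For FGF-19, C4, bile acids and ALT, footnote 16 says "All samples collected Day 1, Weeks 2, 4, 8 and 12 at predose and two samples postdose". Section 8.4.3 and footnote 18 ask for the same pattern for population PK. Footnote 17 asks substudy subjects for predose, 2, 6 and 8 h samples, and names Day 84 for them. The one relaxation visible, in footnote 5, is that "only 1 PK sample will be obtained"; it applies to subjects who discontinue early.

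**What the samples serve.** Section 2.2.2 lists "Pharmacodynamic parameters of EDP-305: FGF19, C4, and bile acid (BA) at Week 12" as a secondary endpoint, and lists Cmax, tmax and AUClast without a week.

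**SAP.** Section 3.2.1 plans at least 10 substudy subjects per group. Table 4 in Section 7.2 runs the Week 12 window to end of treatment plus 7 days. Section 8.8 bins sparse post-dose samples by actual time, with the last bin ending before 9 h. Sections 8.8.1.2 and 8.8.2.2 summarise intensive samples by nominal time and compute PK parameters and FGF19/C4 AUCs for Days 1 and 84.

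**The concern.** A post-dose sample needs a dose that day. On three of the seven permitted visit days the stop rule forbids one, although the sampling footnotes still ask for post-dose draws. Footnote 5 does not help, because a subject who took drug through Day 84 did not discontinue early.

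Two things are at stake. First, that subject's Week 12 profile is lost: Cmax, Tmax and AUClast in the active arms, FGF19 and C4 AUC0–8 and AUC2–8, and the post-dose PD values. Second, a predose sample on Day 86 or 87 is a washout value. Nothing visible in the SAP keeps it out of the Week 12 predose summaries in Sections 8.8.1.1 and 8.8.1.2, the predose PD results, or the all-subject Week 12 plots in Section 8.8.2.4, which set predose concentration against ALT, lipids and other markers.

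**Working it through.** The plan gives no figure to reproduce here. The check is day arithmetic, then the precision cost under assumed losses.

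**Step 1: time since last dose.** Inputs: window Days 81–87 (Table 19); last dose on Day 84 (Section 7.1.4, footnote 3); intensive draws at 2, 6 and 8 h (footnote 17). Assumption: doses and draws at the usual morning time. For a visit on day d after Day 84, hours since last dose = 24 × (d − 84) + nominal hours.

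| Visit day | Dose allowed that day | Predose draw: hours since last dose | Nominal 2/6/8 h draws: hours since last dose |
|---|---|---|---|
| 81–84 | yes | about 24 | 2/6/8 |
| 85 | no | 24 | 26/30/32 |
| 86 | no | 48 | 50/54/56 |
| 87 | no | 72 | 74/78/80 |

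A Day 85 predose sample is still a 24 h trough; those on Days 86 and 87 are not. Three of seven window days is a count of days, not the chance of a late visit.

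**Step 2: what the visible SAP text does with such a visit.** Days 85–87 are 1–3 days after end of treatment, inside the 7-day allowance in SAP Table 4, so the visit keeps its Week 12 label.
- Sparse: times of 24 h or more lie beyond the last listed bin (below 9 h). The SAP lets bins be modified, but does not define the reference dose when none is given at the visit.
- Intensive: nominal-time summaries and AUCs carry no visible rule for a profile without a dose.
- Predose: there is no visible limit on time since last dose.

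The times needed to recognise these cases are collected. Section 8.4.3 has actual PK sample times entered in the eCRF and says "the site should record the time of last dose taken at home prior to the visit".

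**Step 3: precision if profiles are lost.** Inputs: n = 10 per group is the SAP minimum; 15 and 20 are assumed. Losses of k = 1, 2 or 3 in one active arm are assumed. The SD is held fixed.

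For the PD comparison with placebo, SE ratio = √[(1/n + 1/(n − k)) / (2/n)]:
- n = 10: √[(1/10 + 1/9)/(2/10)] = 1.027; then 1.061 and 1.102, so +2.7%, +6.1%, +10.2%
- n = 15: 1.018, 1.038, 1.061, so +1.8%, +3.8%, +6.1%
- n = 20: 1.013, 1.027, 1.043, so +1.3%, +2.7%, +4.3%

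For one arm's mean, which suits the descriptive PK parameters, SE ratio = √[n/(n − k)]. At n = 10: 1.054, 1.118, 1.195, so +5.4%, +11.8%, +19.5%.

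**The case against.** **Day 84 is already named.** Footnote 17 uses Days 1 and 84 for the 2/6/8 h draws but week labels for Weeks 2, 4 and 8, and SAP 8.8 also says Days 1 and 84. A site could read this as fixing the profile to Day 84. That weakens the point for the substudy. But no visible text narrows the ± 3 days for substudy visits, and the reading does not help the sparse samples.

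**A site may dose anyway.** Section 5.7 and footnote 19 support giving the dose in clinic. A reader might therefore infer that the loss is certain, or that there is none. Neither follows. The stop rule addresses late visits specifically and is the more natural one to follow, but this is partly a conflict of instructions.

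**A rule may exist out of sight.** Text is redacted in Sections 5.7, 5.7.1, 7.1.3, 8.4.6 and 8.4.7 and in SAP 8.9, and the Pharmacy, Laboratory and Study Manuals are not available. This stands as a limit on the claim. The redaction in Protocol footnote 18 can be resolved: the SAP's copy concerns subjects with liver injury who remain on drug.

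**The endpoints survive.** Largely true. The PK endpoint has no week attached, is summarised descriptively, and is also served by Day 1. Section 8.4 centres the FGF-19, bile acid and C4 draws on fasting predose samples, and a Day 85 predose sample is sound. SAP 7.3.1 leaves missing secondary data unimputed, which covers a missing profile but not an undosed or washout sample that was collected.

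**Conclusion.** The inconsistency is in the current text and worth correcting, but it is minor. A compliant visit on Days 85–87 under the stop rule loses its Week 12 post-dose samples; on Days 86–87 it also yields a 48 or 72 h value that the visible SAP text would treat as a Week 12 predose result. The loss is confined to some substudy profiles (PK parameters, FGF19/C4 AUC0–8 and AUC2–8), post-dose PD values and those late troughs.

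The 2.7–10.2% rise in standard error rests on the minimum substudy size, a fixed SD and an assumed 1–3 losses in one arm. The true number of late visits is unknown and could be zero.

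Three stronger readings are not supported:
- **Mislabelled intensive profiles.** Values drawn 26–80 h after the last dose enter the AUCs only if a site makes the draws without a dose, and recorded times would identify them.
- **Damage to the primary analysis.** A Week 12 ALT value can still be drawn on Days 85–87, falls in the SAP window and needs no dose that day.
- **Failure of the secondary PK endpoint.** Day 1 profiles are untouched, as are Week 2–8 samples.

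**What to change.** **Protocol.** Schedule the Week 12 PK/PD visit, at least for substudy subjects, on Days 81–84 with that day's dose given in clinic. Align Section 7.1.4, Section 5.7 and Table 19 footnotes 3 and 16–19, and the copy of the schedule in the SAP.

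**SAP 8.8.** Exclude from the Week 12 nominal-time and AUC analyses any profile without a dose that day. Exclude, or label separately, predose samples taken well beyond 24 h after the last dose, against a stated limit. Identify both from recorded dose and sample times, and report the numbers by group.

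**Cost.** A four-day instead of a seven-day window for these subjects, plus short text changes. No extra dosing. Late attenders are still lost.

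**An option for the sponsor, not the lead change.** Dosing could continue to the actual visit, at most 3 more days (3/84 = 3.6%). This would recover late attenders, but it changes exposure before the ALT assessment for some subjects. Because Section 7.1.5 places "the EOS visit 4 weeks after the last dose of study drug for follow-up safety assessments", EOS would move to Day 113, 114 or 115 (85, 86 or 87 + 28); only Day 115 misses the Day 110–114 window. Whether dispensed supply reaches Day 87 cannot be seen.
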